5.2.3 Health economic objectives

To determine incremental cost per quality-adjusted life year (QALY) between treatment arms.

5.3 Trial design

An open-label, multicentre, randomised, single-period, two-arm parallel group trial with Stage 1 (internal pilot) to test the feasibility of recruitment and randomisation followed by the Stage 2 (substantive study) if the progression criteria are met.

422 pregnant women aged 16 years and over with EOT2D diagnosed prior to or during current pregnancy will be recruited through outpatient antenatal diabetes clinics. Women fulfilling the eligibility criteria will be randomised to real-time continuous glucose monitoring (CGM) or to continue with standard care self-monitoring blood glucose (SMBG) (finger-prick testing). It is expected that continuous glucose monitoring will be increasingly used in routine care for women with EOT2D, particularly for those who are treated with insulin. The study will take place within the home and NHS routine antenatal clinical settings.

5.3.1 Internal pilot

An internal pilot will recruit 142 women over 12 months to address the feasibility of recruiting and retaining pregnant women with T2D from geographically representative sites, and their willingness to use CGM.

The Trial Management Group (TMG) with PPI partner participation will review progress, reporting to the Data Monitoring Committee (DMC) and Trial Steering Committee (TSC). At the end of the 12-month pilot period, an assessment of CGM sensor usage, availability of CGM glucose data for the primary maternal outcome (CGM time-in-range) and the event rate for the neonatal composite outcome (neonatal care admission and perinatal mortality) for those who have given birth will be available for review. Acceptability of the trial processes will be considered.

6 Methods

6.1 Site selection

The trial sponsor has overall responsibility for site and investigator selection and has delegated this role to the CIs and NCTU.

6.1.1 Study setting

Recruitment for this study will take place in UK NHS antenatal diabetes clinics. Participants will use the CGM until after delivery of their babies, in their usual day-to-day setting, with support from their usual clinical care team.

Interviews will be conducted either by telephone, videocall or face to face at a mutually convenient location.

6.1.2 Site/Investigator eligibility criteria

20 NHS maternity clinics with specialist diabetes pregnancy teams serving mixed ethnic lower income groups representative of the diversity of pregnant women with T2D will be selected.

Trial sites will be issued with a copy of this protocol along with a pack of documentation needed by the Research and Development Department (R&D) of their Trust to enable the Trust to provide confirmation of capacity and capability to undertake the study.

6.1.2.1 Principal Investigator's (PI) qualifications and agreements

The investigators must be willing to sign an investigator statement to comply with the protocol for this trial (confirming their specific roles and responsibilities relating to the trial, and that their site is willing and able to comply with the requirements of the trial). This includes confirmation of appropriate qualifications and training, agreement to comply with the principles of GCP, to permit monitoring and audit as necessary at the site, and to maintain documented evidence of all staff at the site who have been delegated significant trial related duties.

6.1.2.2 Resourcing at site

The investigators should be able to demonstrate a potential for recruiting the required number of suitable participants within the agreed recruitment period (i.e., the investigators regularly treat the target population). They should also have an adequate number of qualified staff and facilities available for the foreseen duration of the trial to enable them to conduct the trial properly and safely.

Sites will be expected to complete a delegation of responsibilities log and provide staff contact details.

The site should have sufficient data management resources to allow prompt data return.

6.2 Site approval and activation

Each site will undergo site initiation. Following initiation and on receipt of the signed investigator statement, approved delegation of responsibilities log, staff contact details, and appropriate local approvals, written confirmation of site activation will be sent to the site PI. Sites will not be permitted to recruit any patients until a letter for activation has been issued. The Trial Manager or delegate will be responsible for issuing this after a green light to recruit process has been completed.

The site must conduct the trial in compliance with the protocol as agreed by the Sponsor, HRA and favourable opinion given by the Research Ethics Committee (REC). The PI or delegate must document and explain any deviation from the approved protocol and communicate this to the trial team at NCTU.

A list of activated sites may be obtained from the Trial Manager.

6.3 Participants

6.3.1 Participant recruitment

Potential participants will be identified by their clinical care team, provided with study information either in person or by post/email and invited to join the study. They may also contact the clinical care team directly. All women will be offered the opportunity to discuss the advantages and disadvantages of study participation with a member of the research team and/or their diabetes physician/diabetes educator/obstetric physician/obstetrician. They will usually have 24 hours or more to consider involvement prior to consenting, however due to the low-risk and routine nature of the intervention, and the need to keep the participant burden to a minimum, the participant may be consented at the initial contact if the hospital team feels that they are fully informed. There will be **NO EXCEPTIONS** (waivers) to eligibility requirements at the time of enrolment or randomisation. Questions about eligibility criteria should be addressed PRIOR to attempting to enrol the participant.

The eligibility criteria for this trial have been carefully considered and are the standards used to ensure that the study population are representative of those with T2D pregnancy and medically appropriate participants are entered. Participants not meeting the criteria should not be entered into the trial for their safety and to ensure that the trial results can be appropriately used to make future treatment decisions for other people with similar diseases or conditions. It is therefore vital that exceptions are not made to these eligibility criteria.

Participants will be considered eligible for enrolment in this trial if they fulfil all the inclusion criteria and none of the exclusion criteria as defined below.

6.3.1.1 Participant inclusion criteria

- 1. Type 2 diabetes (T2D)
- 2. 16 years of age or over
- 3. Confirmed pregnancy
- 4. HbA1c of \geq 43 mmol/mol (6.1%) in pregnancy (prior to randomisation)
- 5. Willingness to use the study devices throughout the trial
- 6. Able to provide informed consent
- 4 days (aiming for ≥96 hours) of baseline CGM data before randomisation at no later than 16+0 weeks' gestation. In cases where 72-96 hours of CGM data is available, inclusion may be approved by the NCTU team.

6.3.1.2 Participant exclusion criteria

- 1. Non-type 2 diabetes
- 2. Chronic kidney disease (CKD) grade 4 or 5 (GFR <30ml/min)

6.3.1.3 Inclusivity

For the purpose of this protocol, whilst we refer to pregnant women throughout, the study is inclusive of non-binary, gender-fluid, or any other pregnant persons.

6.3.1.4 Retention

Participants will remain in the trial for the duration of their pregnancy until maternal discharge after delivery, with data collected on their baby(ies) until neonatal discharge, if admitted (or 28 days post-delivery if admission prolonged). During pregnancy, participants will be seen by the clinical research team on a 4-weekly basis.

6.3.1.5 Co-enrolment guidance

Co-enrolment into interventional diabetes studies which could impact maternal glucose levels is not permitted, however co-enrolment is permitted for observational studies and / or studies which do not impact on maternal glucose, with approval from TMG.

6.3.2 Eligibility criteria for individuals performing the interventions

The intervention will be conducted by site staff who are experienced in working with pregnant women with T2D. Full training in the study procedures will be provided to the local study team.

6.3.3 Screening procedures and pre-randomisation investigations

Written informed consent to enter and be randomised into the trial must be obtained from participants after explanation of the aims, methods, benefits and potential hazards of the trial and **BEFORE** any trial-specific procedures. The only procedures that may be performed in advance of written informed consent being obtained are those that would be performed on all patients in the same situation as a usual standard of care.

6.3.3.1 Screening logs

Participating sites will be expected to maintain records of all patients screened for the trial, including those who are not entered (for whom ID numbers are not obtained) either due to ineligibility or because the patient declined to participate.

6.4 Interventions

Women fulfilling the eligibility criteria will be randomised to real-time study CGM or to continue with standard care glucose monitoring.

6.4.1 Intervention arm

6.4.1.1 Products

Women assigned to the intervention arm will monitor their glucose levels using a CE marked real-time CGM, **FreeStyle Libre 3** (Abbott Diabetes Care, Inc.), using the FreeStyle Libre apps installed on their smartphone. A mobile phone to host the apps will be provided if the participant does not have a compatible smartphone device.

6.4.1.2 Accountability

The local PI will ensure that adequate training is provided to the participants by the hospital team.

6.4.1.3 Treatment schedule

Participants will use the CGM throughout pregnancy until after delivery of their baby(ies). The CGM sensor will need to be replaced every 14 days. If participants lose the ability to access the CGM data during the trial they should revert to their pre-trial method of glucose monitoring.

The CGM glucose measures will be reviewed at study visits during pregnancy. As CGM data is uploaded and shared in real-time, measures may also reviewed by the clinical care and research teams at any time.

Ongoing care (post-delivery) will be at the discretion of the treating team.

6.4.2 Control arm

6.4.2.1 Products

Participants randomised to the control arm will wear a masked Freestyle Libre sensor (Pro, Libre 3, or equivalent) at 20, 28, 32 and 36 weeks' gestation to provide comparable outcome data. CGM data from masked sensors are available to researchers (CTU team, study statisticians, non-clinical members of the local research team) and will not routinely be available to participants or treating clinical teams.

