6.6.1.7 Study visits

Follow up visits will be every 4 weeks at ~16/40, 20/40, 24/40, 28/40, 32/40, 36/40 (+/- 2 weeks). It is expected that the majority of ongoing study visits will align with routine NHS antenatal clinic visits however virtual study visits (e.g., using phone or video calls) will be offered if appropriate, and data from community appointments may be used if needed.

At these visits the following data will be recorded on the study database:

- Weight
- Blood pressure
- Glucose monitoring method(s), frequency of glucose testing
- Insulin delivery method(s), dose and type, if relevant
- Other diabetes treatment

• Adverse events of special interest

In addition to the data collected above (6.6.1.7), the following will be performed at key visits:

- Masked CGM for control group participants (14 days data collection) at 20, 28, 32, and 36 weeks' gestation
- Blood collection for HbA1c at 28, 32, and 36 weeks' gestation
- Follow-up questionnaires at 32 weeks' gestation

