6.10.4 Statistical methods

6.10.4.1 Primary outcome analysis

Maternal glucose:

The primary analysis will evaluate the change in the time spent in the target glucose range (CGM TIR 3.5-7.8 mmol/L) between the intervention and control arm between 20 weeks' gestation and 38 weeks or until delivery (if delivered earlier), based on 4 x 14-day CGM assessments, at 20-22, 28-30, 32-34 and 36-38 weeks. The median gestation of delivery in T2D pregnancy is 38 weeks. A linear mixed effects regression model will be fit with CGM TIR from 20 weeks' gestation until delivery as the dependent variable adjusting for baseline CGM TIR, and subject as random effects. A point estimate, 95% confidence interval and p-value will be reported for the treatment effect based on the linear regression model. Residual values will be examined for an approximate normal distribution. If values are highly skewed, then a transformation or robust statistical methods will be used instead.

Neonatal outcomes:

The primary neonatal outcome is a composite of neonatal unit admission or death in line with section 6.10.4.3.

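### Primary time in range is not collected alike in the two arms: control may use another sensor model, and visits at ±2 weeks do not fit the fixed 14-day windows

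*Protocol*

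**What the plan says.** **Device.** Section 6.4.1.1: "Women assigned to the intervention arm will monitor their glucose levels using a CE marked real-time CGM, FreeStyle Libre 3". Section 6.4.1.3 adds: "Participants will use the CGM throughout pregnancy until after delivery of their baby(ies"). For control, section 6.4.2.1 says that participants "will wear a masked Freestyle Libre sensor (Pro, Libre 3, or equivalent") at 20, 28, 32 and 36 weeks. The stated aim is outcome data comparable between arms. What counts as equivalent is not defined, and nothing requires one model across arms.

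**Timing of control sensors.** Section 6.6.1.7 lists "Masked CGM for control group participants (14 days data collection) at 20, 28, 32, and 36 weeks' gestation". The same section sets the visits: "Follow up visits will be every 4 weeks at ~16/40, 20/40, 24/40, 28/40, 32/40, 36/40 (+/- 2 weeks"). The schedule table in section 6.6 repeats the two-week tolerance for the 28-, 32- and 36-week columns, which include the masked sensor row. Its column for weeks 16, 20 and 24 shows no tolerance.

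**Analysis.** Section 6.10.4.1 makes the primary maternal analysis "based on 4 x 14-day CGM assessments, at 20-22, 28-30, 32-34 and 36-38 weeks". Further on, the same section describes the model with "CGM TIR from 20 weeks' gestation until delivery as the dependent variable". Section 6.5.1 ends the outcome at 38 weeks, or at delivery if that is earlier.

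**Women who stop trial CGM.** Section 6.4.6 and a footnote to the section 6.6 table provide for masked sensors at the key timepoints in intervention women who have stopped the trial device.

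**The concern.** TIR counts readings between two fixed cut-offs. If mean glucose lies close to the upper one (7.8 mmol/L), a small calibration difference between sensor models moves a noticeable share of readings across it. After randomisation the model follows the allocation, so randomisation does not balance it. Baseline TIR does not help either: the baseline sensor is masked in all women before allocation, so it carries no information about a difference that arises later in one arm.

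Timing is a second, separate route. Data from a woman wearing trial CGM can be cut to any gestational window afterwards. A control profile exists only for the days when the sensor was worn. If those days miss the window, the profile is either lost in part or compared with a different gestation. Both routes act mainly on control data in one of the two primary outcomes.

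**Working it through.** **1. The plan's own figure.** Inputs from section 6.7: SD 20 points, two-sided 5%, 90% power, 380 analysable, so 190 per arm at 1:1.

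- Standard error = 20 × √(2/190) = 2.052.
- Detectable difference = (1.960 + 1.282) × 2.052 = 6.65 points. This matches the protocol.
- For a 10-point difference: 85 per arm, 170 in total, and 170/0.9 = 188.9, against the stated 188. The sample size is not in question.

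**2. Sensor model (assumed inputs).** The documents give no glucose mean, CV or between-model offset. I assume lognormal glucose with mean 7.2-7.6 mmol/L and CV 25-30%. This gives TIR of about 59-67%, close to the protocol's expected 60% in control.

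- TIR = P(3.5 ≤ glucose ≤ 7.8), recomputed after shifting every reading by the offset.
- Example, mean 7.4 and CV 25%: TIR is 63.0%. A shift of +0.2 mmol/L lowers it by 3.9 points, and a shift of −0.2 raises it by 3.6.
- Over the whole grid, a 0.2 mmol/L offset moves TIR by 2.4 to 4.1 points.

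This assumes that every control window is on the offset model. If a fraction f is affected, the shift in the arm mean is f times as large. With f = 0.3 it is 0.3 × 2.4 = 0.7 to 0.3 × 4.1 = 1.2 points.

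**3. What a net artefact of b points would do.** With z = b/2.052, the two-sided error is Φ(−1.96 + z) + Φ(−1.96 − z). If the artefact works against a true effect of 6.65 points, power is Φ((6.65 − b)/2.052 − 1.96).

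| Assumed net artefact b | Error rate with no true effect | Power for a true 6.65, artefact opposing |
|---|---|---|
| 0 | 5% | 90% |
| 1 | 7.8% | 79% |
| 2 | 16% | 62% |
| 3 | 31% | 43% |

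**4. Timing (document figures only).** A 14-day sensor fitted s days off the nominal week overlaps its window by max(0, 14 − |s|) days.

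| Days off nominal | Window days covered, of 14 |
|---|---|
| 0 | 14 |
| 3 | 11 |
| 7 | 7 |
| 10 | 4 |
| 14 | 0 |

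At the permitted limits:

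- A late 36-week sensor runs from 38 to 40 weeks, past the end of the outcome period. An early one runs from 34 to 36.
- A late 28-week sensor and an early 32-week sensor both cover 30-32 weeks, which lies in none of the four windows.

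The actual spread of visits is not given. If placement were uniform over ±14 days, mean overlap would be 196/29 = 6.8 of 14 days (48%). Over ±7 days it would be 154/15 = 10.3 days (73%).

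**5. Wording of the dependent variable.** Four 14-day sensors cannot supply TIR for the whole period from 20 weeks to delivery. Section 6.10.4.1 therefore describes two different quantities, and the one that runs to delivery also disagrees with the 38-week limit in section 6.5.1.

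**The case against.** **No bias is shown.** Another model in control is permitted, not required, and Libre 3 is on the same list. The documents do not say how often another model is used, or that models differ in any direction. This stands. A reader might infer that an artefact as large as the detectable difference is likely, but that needs a larger offset in every control window, and the documents support neither.

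**The asymmetry is not absolute.** A reader might infer that all intervention TIR comes from Libre 3, that it always fills the exact window, and that only control is affected. The documents do not support that: intervention women who stop trial CGM wear masked sensors at the same visits, under the same tolerance. This stands too, and it limits the point to a difference of degree.

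**The timing loss is usually partial.** Complete loss of a window occurs only at the two-week limit, and the tolerance is attached to visits. It reaches the sensors because they are fitted at those visits. For 20 weeks it rests on section 6.6.1.7 alone, so a sensor worn at 18-20 weeks is the weakest example. Bias, as distinct from lost data, also needs TIR to change with gestation and placement to lean early or late. Neither is documented.

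**Handling of off-window data belongs in the SAP.** In part. Mapping rules and sensitivity analyses commonly sit there, and their absence is no fault. But the protocol itself fixes the device list, the visit tolerance and the windows, and the tolerance does not fit the windows. An SAP cannot recover control days that were never recorded.

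**Conclusion.** The point holds as a difference in how the primary maternal outcome is measured and as a conflict between timing rules that the protocol itself states. It does not show that the comparison is biased.

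The sensor part rests on an assumed offset and an unknown frequency of use. Under the stated assumptions, 0.2 mmol/L in every control window corresponds to 2.4-4.1 TIR points against a detectable 6.65, falling in proportion to the share of windows affected.

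The timing part needs no outside figures: overlap falls one day for each day off nominal, and a late 36-week sensor runs past the 38-week limit. How many profiles this touches cannot be known from the protocol.

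It is worth acting on because a primary outcome is involved, the remedy is cheap, and it works best while windows are still being collected.

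**What to change.** **Sensor model**

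- Use masked Libre 3, which section 6.4.2.1 already allows, for the remaining masked outcome windows in both arms where supply permits.
- Define what counts as equivalent, and record the model for each window.
- Pre-specify a sensitivity analysis restricted to windows on Libre 3. State that this subset is not protected by randomisation, because model may vary with site or calendar time.

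**Timing**

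- Replace the mismatch between visit tolerance and analysis windows with one rule in gestational days: the same tolerance in both arms, truncated at 38 weeks.
- Then either cut continuous intervention data to a matching distribution of gestational days, or include gestational age at the window mid-point in the model.
- Reword the dependent variable in section 6.10.4.1 so that it agrees with the four windows and the 38-week limit.

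**Cost.** A supply choice within what is already permitted, one data field, a short protocol clarification and SAP text. The sample size does not change. The downsides are small: dependence on Libre 3 supply, and loss from the sensitivity analysis of windows already collected on other models.

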6.4.2.3 Control schedule

Participants will continue to monitor their glucose via the **routine clinical care** method throughout pregnancy:

• SMBG (finger-prick testing) 4-7 times a day, recording in a paper or electronic diary format (as provided locally).

Participants using continuous glucose monitoring in later pregnancy will be asked to continue wearing masked sensors at the key timepoints, and may be asked to share their non-study sensor glucose data with the trial team.

6.4.3 Dispensing

Trial CGM sensors will be provided to the study team at each participating centre and additional devices should be requested by sites as appropriate. Sensors provided for use in the trial should be used for PROTECT participants only. Usage of devices will be monitored.

Participants will be able to keep any remaining CGM sensors at the end of the study.

6.4.4 Compliance and adherence

Compliance with CGM use will be monitored by the clinical care team during trial and standard antenatal visits which will take place either face-to-face or virtually 4-weekly between 12 weeks until delivery.

6.4.5 Concomitant care

Concomitant care will be as per usual clinical practice.

6.4.6 Treatment discontinuation

In consenting to the trial, participants are consenting to trial interventions, trial follow-up and data collection. However, an individual participant may stop treatment early or be stopped early for any of the following reasons (not exhaustive):

- Unacceptable adverse event
- Any change in the participant's condition that in the clinician's opinion justifies the discontinuation of treatment
- Withdrawal of consent for treatment by the participant
- Significant protocol violation or non-compliance

As participation in the trial is entirely voluntary, the participant may choose to discontinue trial treatment at any time without penalty or loss of benefits to which they would otherwise be entitled. Although not obliged to give a reason for discontinuing their trial treatment, a reasonable effort should be made to establish this reason, whilst remaining fully respectful of the participant's rights.

Participants who discontinue protocol treatment, for any of the above reasons, should remain in the trial for the purpose of follow up, and data collection (including masked CGM sensor data at key timepoints for both intervention and standard care participants), and analysis, if they are willing.

